28. The PROMIS Physical Functioning Scale and the EQ-5D-5L Health Scale will be assessed during the screening period (within 14 days prior to randomization), on C1D1 (-1 day), C2D1 (± 7 days), C3D1 (± 7 days), C4D1 (± 7 days), C5D1 (± 7 days), C6D1 (± 7 days) and C7D1 (± 7 days), respectively. C1D1 assessments should be completed prior to dosing. The mean score of evaluations during the screening period (within 14 days prior to randomization) and on C1D1 will be used as baseline. The PROMIS Physical Functioning Scale includes two different sets of topics for the upper and lower extremities. Items assessing lower extremity function will be used for patients with lower extremity tumors, and the items for assessing upper extremity function will be used for patients with upper extremity tumors. On visit days when scales are required, including the screening period, it is recommended to be completed before any invasive clinical procedure is performed. Even if a patient experiences disease progression or discontinues treatment, PROMIS Physical Functioning Scale and the EQ-5D-5L Health Scale are recommended to be completed from baseline up to week 25.

29. NCI-PRO-CTCAE will be assessed during the screening period (within 14 days prior to randomization), on C1D1 (-1 day), C1D8(± 1 days), C1D15 (± 1 days), C1D22 (± 1 days), C2D1 (± 2 days), C2D8(± 2 days), C2D15 (± 2 days), and C2D22 (± 2 days), C3D1 (± 7 days), C4D1 (± 7 days), C5D1 (± 7 days), C6D1 (± 7 days), C7D1 (± 7 days), and EOT visit respectively.
30. Patient who completed the C7D1 visit of Part 1 will be further confirmed by the investigator whether to enter Part 2 and receive treatment with open-label ABSK021. Patients need to meet eligibility criteria to continue in Part 2. The investigator will comprehensively evaluate the benefits and risks of the patient entering Part 2, and make the final decision based on the principle of maximizing the patient's benefit-risk ratio. In principle, a maximum of 28 days is allowed from the end of C7D1 follow-up in Part 1 to entry into Part 2.

Table 2: Schedule of Events - Part 2

Study Procedure	Cycle 1 ¹	Cycle 2	Cycle 3	Cycle 4 ²	Cycle 7	End of Treatment Visit (EOT Visit) ³	Safety Follow-up ⁴	Progression Follow-up ⁵
	C1D1 (- 2 days)	C2D1 (± 7 days)	C3D1 (± 7 days)	C4D1 (± 7 days)	C7D1 (± 7 days)			
	Week 25	Week 29	Week 33	Week 37	Week 49			
Part 2 eligibility confirmation ¹	X							
Physical examination/ECOG score ⁶	X	X	X	X	X	X		
Vital Signs ⁷	X	X	X	X	X	X		

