Clinical laboratory tests								
Pregnancy test ⁸	X			X	X	X		
Hematology ⁹	X	X	X	X	X	X		
Blood chemistry ¹⁰	X	X	X	X	X	X		
Myocardial Enzyme Test ¹¹	X	X	X	X	X	X		
Coagulation ¹²				X	X	X		
Urinalysis ¹³	X	X	X	X	X	X		
Thyroid function tests ¹⁴				X	X	X		
12-lead ECG ¹⁵	X	X	X	X	X	X		

Study Procedure	Cycle/Day	Cycle 1 ¹	Cycle 2	Cycle 3	Cycle 4 ²	Cycle 7	End of Treatment Visit (EOT Visit) ³	Safety Follow-up ⁴	Progression Follow-up ⁵
		C1D1 (- 2 days)	C2D1 (± 7 days)	C3D1 (± 7 days)	C4D1 (± 7 days)	C7D1 (± 7 days)			
		Week 25	Week 29	Week 33	Week 37	Week 49			
Echocardiography/MUGA ¹⁶		X			X	X	X		
Adverse Event Reporting ¹⁷		X	X	X	X	X	X	X	
Concomitant Medications and Concomitant Therapies ¹⁸		X	X	X	X	X	X	X	
Dispensing of ABSK021 ¹⁹		X	X	X	X				
PK Sample Collection ²⁰					X	X	X		
Tumor Imaging Assessment ²¹					X	X	X		X
ROM of affected joints ²²					X	X	X		
Worst Stiffness NRS and BPI Worst Pain NRS ²³		X	X	X	X	X	X		
PROMIS Physical Functioning Scale ²⁴		X	X	X	X	X	X		
EQ-5D-5L Health Scale ²⁴		X	X	X	X	X	X		
Pre-Part 3 Evaluation ²⁵						X			
New anti-tumor therapy after discontinuation of study drug								X	X

Abbreviations: ALT= Alanine transaminase; AST= Aspartate transaminase; APTT= activated partial thromboplastin time; BUN= Blood urea nitrogen; CK= creatine phosphokinase; CK-MB= phosphocreatine kinase isoenzyme; ECG= electrocardiogram; ECOG= Eastern Cooperative Oncology Group; EOT= End-of-Treatment; Fbg=fibrinogen; LDH= lactate dehydrogenase; MRI=

magnetic resonance imaging; MUGA= multigated acquisition scans; PK= Pharmacokinetic; PS= Performance status; TSH= Thyroid stimulating hormone; FT3= Free triiodothyronine; FT4= Free Thyroxine; WBC= white blood cells.

Footnote:

Additional unscheduled safety or efficacy assessments may be performed as clinically indicated to determine the relationship between events and/or the duration of the event. All time windows in the table are for visits and not for administration.

1. C1D1 of Part 2 (P2-C1D1) is defined as the day of Part 2 eligibility confirmation and the first dose of Part 2, and if any test to be performed at Part 2 C1D1 visit has been done at Part 1 C7D1 visit or the latest visit before Part 2 C1D1, with an interval no more than 7 days, repeated tests are not required on C1D1 of Part 2.
2. After completing the Cycle 4 (i.e., Week 37) visit of Part 2, patients will return to the study site for a visit every 12 weeks (± 7 days) with the next visit date of C7D1 ± 7 days.

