23. Patients should complete BPI-Worst-Pain-NRS and Worst-Stiffness-NRS on C1D1 (at least 4 of 7 consecutive days within ± 7 days), C2D1 (at least 4 of 7 consecutive days within ± 7 days), C3D1 (at least 4 of 7 consecutive days within ± 7 days), C4D1 (at least 4 of 7 consecutive days within ± 7 days) and C7D1 (at least 4 of 7 consecutive days within ± 7 days). If the assessment to be performed at Part 2 C1D1 visit has been done at Part 1 C7D1 visit or the latest visit before P2-C1D1, with an interval of no more than 7 days, repeated assessments are not required on C1D1 of Part 2. On the days when a Numerical Rating Scale is required, it is recommended to be completed prior to any invasive clinical procedure.
24. The PROMIS Physical Functioning Scale and the EQ-5D-5L Health Scale will be assessed on C1D1 ($+ 7$ days), C2D1 (± 7 days), C3D1 (± 7 days), C4D1 (± 7 days), and C7D1 (± 7 days), respectively. The PROMIS Physical Functioning Scale includes two different sets of topics for the upper and lower extremities. Items assessing lower extremity function will be used for patients with lower extremity tumors, and the items for assessing upper extremity function will be used for patients with upper extremity tumors. If the assessment to be performed at Part 2 C1D1 visit has been done at Part 1 C7D1 visit or the latest visit before P2-C1D1, with an interval of no more than 7 days, repeated assessments are not required on C1D1 of Part 2. On visit days when scales are required, it is recommended to be completed before any invasive clinical procedure is performed.
25. Patient who completed the C7D1 visit of Part 2 will be further confirmed by the investigator whether to enter Part 3 and continue to receive treatment with open-label ABSK021. Patients need to meet eligibility criteria to continue in Part 3. The investigator will comprehensively evaluate the benefits and risks of the patient entering Part 3, and make the final decision based on the principle of maximizing the patient's benefit-risk ratio. In principle, a maximum of 28 days is allowed from the end of C7D1 follow-up in Part 2 to entry into Part 3.

Table 3: Schedule of Events - Part 3

Study Procedure	Cycle 1 ¹	Cycle 4	Cycle 7	Cycle 13 ²	≥ Cycle 19	End of Treatment Visit (EOT Visit) ³	Safety Follow-up ⁴	Progression Follow-up ⁵
	C1D1 (- 2 days)	C4D1 (± 7 days)	C7D1 (± 7 days)	C13D1 (± 14 days)	≥ C19D1 (± 14 days)			
	Week 49	Week 61	Week 73	Week 97	≥ Week 121			

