5.4 Treatment duration

The Part 1 study consists of a screening period (within 28 days prior to randomization) and a treatment period of 6 cycles (28 days/cycle, 24 weeks in total). The primary endpoint analysis will be performed after the last patient has completed Week 25 follow-up and tumor assessments (including Investigator assessment and BIRC assessment).

The Part 2 study consists of a treatment period of 6 cycles (28 days/cycle, 24 weeks in total). Patients who complete Part 2 treatment will be eligible to enter Part 3 to continue a longer period of treatment and safety follow-up.

Part 3 is an extension treatment phase. All patients will continue to receive open-label ABSK021 continuously (28 days per cycle) until any of the following events occur: disease progression, experiencing unacceptable toxicity, withdrawal of informed consent form, commercialization of the study drug for the treatment of TGCT approved by the local regulatory authorities, decision by the sponsor to terminate the study, or until 2 years after the last patient enters Part 3, whichever

occurs first.

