4.2.4. Definition of Analysis Windows

The window for the visits following baseline will be constructed in such a way that the upper limit of the interval falls halfway between the two visits (the lower limit of the first post-baseline

Statistical Analysis Plan for Protocol ABSK-021-301

visit will be Day 2). If an even number of days exists between two consecutive visits then the upper limit will be taken as the midpoint value minus 1 day.

The following rules will be applied to assign actual patient visits to protocol-specified visits. For each protocol-specified study visit, a target study day will be identified to represent the corresponding visit along with a window around the target day. Windows will be selected in a non-overlapping fashion so that a collection date does not fall into multiple visit windows. If a patient has two or more actual visits in one visit window, the visit closest to the target day will be used for analysis. If two visits are equidistant from the target day, then the later visit will be used for analysis.

The visit window and the target study day from Part 1 for each protocol-specified visit are displayed in [Table 4.2](#) and [Table 4.3](#) (depending on the different visit schedules of different endpoints).

Table 4.2 Analysis Windows for PRO endpoints and Range of Motion

Study Period	Protocol Specified Visit	Target Day	Visit Window Range [min, max]		
			Worst Stiffness NRS, BPI Worst Pain NRS, PROMIS-PF and EQ-5D-5L	Range of Motion	NCI-PRO-CTCAE
Part 1	Baseline	1[a]	[-28, 1]	[-28, 1]	[-28, 1]
	Week 2 (C1D8)	8			[2,11]
	Week 3 (C1D15)	15			[12, 18]
	Week 4 (C1D22)	22			[19,25]
	Week 5 (C2D1)	29	[2, 43]		[26, 32]
	Week 6 (C2D8)	36			[33,39]
	Week 7 (C2D15)	43			[40, 46]
	Week 8 (C2D22)	50			[47, 53]

Statistical Analysis Plan for Protocol ABSK-021-301

Study Period	Protocol Specified Visit	Target Day	Visit Window Range [min, max]		
			Worst Stiffness NRS, BPI Worst Pain NRS, PROMIS-PF and EQ-5D-5L	Range of Motion	NCI-PRO-CTCAE
	Week 9 (C3D1)	57	[44, 71]		[54, 71]
	Week 13 (C4D1)	85	[72, 99]	[2, 127]	[72, 99]
	Week 17 (C5D1)	113	[100, 127]		[100, 127]
	Week 21 (C6D1)	141	[128, 155]		[128, 155]
	Week 25 (C7D1)	169	[156, 1st dose date of Part 2 or 184]	[128, 1st dose date of Part 2 or 184]	[156, 1st dose date of Part 2 or 184]
Part 2	Week 25 (C1D1)[b]	169	[156, 1st dose date of Part2]		
	Week 29 (C2D1)	197	[1 day after 1st dose date of Part 2, 211]		
	Week 33 (C3D1)	225	[212, 239]		

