	Week 49 (C7D1)	337	[296, 1st dose date of Part 3 or 352]	[296, 1st dose date of Part 3 or 352]	[296, 1st dose date of Part 3 or 352]	[296, 1st dose date of Part 3 or 352]
Part 3	Week 61 (C4D1)	421	[1 day after 1st dose date of Part 3, 463]	[1 day after 1st dose date of Part 3, 463]	[1 day after 1st dose date of Part 3, 463]	[1 day after 1st dose date of Part 3, 463]
	Week 73 (C7D1)	505	[464, 548]	[464, 548]	[464, 548]	[464, 548]
	Week 97 (C13D1)	673	[549, 757]	[549, 757]	[549, 757]	[549, 757]

Statistical Analysis Plan for Protocol ABSK-021-301

Study Period	Protocol Specified Visit	Target Day	Visit Window Range [min, max]			
			Pregnancy test	Hematology / Urinalysis / Physical examination / ECOG	Blood chemistry / Myocardial Enzyme Test / Vital Signs / 12-lead ECG	Coagulation / Thyroid function tests / Echocardiography/MUGA
	Week 121	841	[758, 925]	[758, 925]	[758, 925]	[758, 925]
	+ 24 weeks					

- a. Day of first dose of study drug.
b. Part 2 baseline for placebo arm in Part 1.

If a patient early discontinues from Part 1 and directly enters into Part 2, the following visit window in Part 2 and Part 3 will be recalculated based on the new target study day from Part 2 and displayed in [Table 4.4](#) and [Table 4.5](#) as below.

Table 4.4 Early entering Part 2 Analysis Windows for PRO endpoints and Range of Motion

Study Period	Protocol Specified Visit	Target Day	Visit Window Range [min, max]	
			Worst Stiffness NRS, BPI Worst Pain NRS, PROMIS-PF and EQ-5D-5L	Range of Motion
Part 2	Week 25 (C1D1)[a]	1	[-14, 1]	
	Week 29 (C2D1)	29	[2, 43]	
	Week 33 (C3D1)	57	[44, 71]	
	Week 37 (C4D1)	85	[72, 127]	[2, 127]
	Week 49 (C7D1)	169	[128, 1st dose date of Part 3 or 184]	[128, 1st dose date of Part 3 or 184]

Statistical Analysis Plan for Protocol ABSK-021-301

Study Period	Protocol Specified Visit	Target Day	Visit Window Range [min, max]	
			Worst Stiffness NRS, BPI Worst Pain NRS, PROMIS-PF and EQ-5D-5L	Range of Motion
Part 3	Week 61 (C4D1)	253	[1st dose date of Part 3 +1, 295]	[1st dose date of Part 3 +1, 295]
	Week 73 (C7D1)	337	[296, 380]	[296, 380]
	Week 97 (C13D1)	505	[381, 589]	[381, 589]
	Week 121	673	[590, 757]	[590, 757]
	+ 24 weeks			

a. Day of first dose of Part 2

Table 4.5 Early entering Part 2 Analysis Windows for Safety Endpoints

Study Period	Protocol Specified Visit	Target Day	Visit Window Range [min, max]			

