5.6.1. Duration of Study Drug Exposure

Exposure to the study drug will be defined as:

- Total duration of exposure (day) = min (last dose date, date of death, date of cut-off) – first dose date + 1
- Actual duration of exposure (day) = total planned exposure – total duration of dose interruptions

Statistical Analysis Plan for Protocol ABSK-021-301

The total and actual duration of exposure for ABSK021 will be summarized descriptively. The number and percentage of patients will be summarized by following categories of duration of drug exposure:

- < 1 month, $\geq 1 - < 3$ months, $\geq 3 - < 6$ months, $\geq 6 - < 9$ months, $\geq 9 - < 12$ months, $\geq 12 - 18$ months, $\geq 18 - 24$ months, ≥ 24 months
- ≥ 1 month, ≥ 3 months, ≥ 6 months, ≥ 9 months, ≥ 12 months, ≥ 18 months, ≥ 24 months

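### For ABSK021 patients who complete Part 1, a 15- to 28-day gap before Part 2 makes the SAP's fixed windows misfile the four-weekly Part 2 visits

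*SAP*

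**What the plan says.** **Protocol.** Table 1, footnote 30: "In principle, a maximum of 28 days is allowed from the end of C7D1 follow-up in Part 1 to entry into Part 2". Table 2, footnote 25, gives the same allowance before Part 3: "In principle, a maximum of 28 days is allowed from the end of C7D1 follow-up in Part 2 to entry into Part 3". Table 2, footnote 1, says that Part 2 C1D1 "is defined as the day of Part 2 eligibility confirmation and the first dose of Part 2". Section 5.4 adds: "The Part 2 study consists of a treatment period of 6 cycles (28 days/cycle, 24 weeks in total"). Part 2 visits therefore run from the first Part 2 dose in 28-day steps.

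**SAP 4.2.4.** "The visit window and the target study day from Part 1 for each protocol-specified visit are displayed in" Tables 4.2 and 4.3. The Part 2 targets are Days 197, 225, 253 and 337. In the columns with four-weekly visits the windows are:
- Week 29: "1 day after 1st dose date of Part 2, 211"
- Week 33: Days 212 to 239
- Week 37: Days 240 to 295
- Week 49: Day 296 to the first Part 3 dose, or Day 352

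If two visits share a window, the one nearer the target is used, and the later one if they tie. For patients randomised to ABSK021, Table 4.1 keeps the Part 1 origin throughout Parts 2 and 3. Windows counted from the first Part 2 dose exist in Tables 4.4 and 4.5, but only for one group: "If a patient early discontinues from Part 1 and directly enters into Part 2, the following visit window in Part 2 and Part 3" are recalculated.

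**SAP 5.6.1.** "Total duration of exposure (day) = min (last dose date, date of death, date of cut-off"), less the first dose date, plus one day.

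**The concern.** The Part 2 targets are right only if Part 2 starts on Day 169, the nominal day of Part 1 C7D1. The lower limit of the Week 29 window follows the actual Part 2 dose date, so the authors knew that the start varies. The upper limits 211, 239 and 295 do not follow it. A patient who completes Part 1 and enters Part 2 late, within the protocol's allowance, is not covered by the re-anchored tables.

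At stake are the by-visit PRO, laboratory, vital sign and ECG summaries for the ABSK021 arm beyond Part 1 (SAP 6.6.2 and 7.1; the P1-P3 group of Tables 4.6 and 4.7). A value labelled Week 37 could come from a visit one cycle earlier in Part 2, while the real Week 37 visit goes unused.

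**Working it through.** **Plan's own limits.** SAP 4.2.4 sets each upper limit halfway between consecutive targets. This reproduces the tables: (197+225)/2 = 211; (225+253)/2 = 239; (253+337)/2 = 295.

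**Visit days.** Let g be the days from Part 1 C7D1 (taken as Day 169) to the first Part 2 dose. On-schedule visits fall at C2D1 = 197+g, C3D1 = 225+g, C4D1 = 253+g and C7D1 = 337+g.

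| g | C2D1 | C3D1 | C4D1 | Used for Week 29 / 33 / 37 |
|---|---|---|---|---|
| 0 | 197 | 225 | 253 | C2D1 / C3D1 / C4D1 |
| 14 | 211 | 239 | 267 | C2D1 / C3D1 / C4D1 |
| 15 | 212 | 240 | 268 | none / C2D1 / C3D1 |
| 28 | 225 | 253 | 281 | none / C2D1 / C3D1 |

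At g = 15, C3D1 and C4D1 both lie in the Week 37 window. C3D1 is 253−240 = 13 days from target and C4D1 is 268−253 = 15 days, so C3D1 is used. In general the distances are 28−g and g, so C3D1 wins for every g from 15 to 28. At g = 28 the Week 29 window is Days 198 to 211, while C2D1 is due on Day 225 and, even 7 days early, falls on Day 218. The window cannot hold its own visit.

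**Threshold.** With the ±7-day allowance on Part 1 C7D1, the gap needed runs from 8 days (C7D1 on Day 176) to 22 days (Day 162). If efficacy days are counted from randomisation, up to 3 days before first dose, the nominal 15 becomes as low as 12.

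**Which columns.** Affected: the PROs in Table 4.2; in Table 4.3, hematology/urinalysis/physical examination/ECOG and chemistry/myocardial enzymes/vital signs/ECG. Range of motion, pregnancy test and coagulation/thyroid/echocardiography have no Week 29 or 33 window. Their C4D1 is at most Day 281, inside the limit of 295, so Week 37 is kept.

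**Week 49.** 337+g exceeds 352 from g = 16. If the patient enters Part 3, the window extends to the first Part 3 dose and C7D1 is kept. Only without Part 3 entry does it fall outside every window.

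**Part 3.** One 28-day gap gives C4D1 on Day 449 (limit 463), C7D1 on Day 533 (limit 548) and C13D1 on Day 701 (limit 757); none moves. The two gaps must total 43 days before C4D1 leaves its slot (421+43 = 464).

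**Frequency, by assumption only.** The documents give no gap distribution. Simulating 200,000 patients with Part 1 C7D1 and each Part 2 visit uniform within ±7 days:
- Gap uniform over 0 to 28 days: C2D1 lands in Week 29 in 52%, and C4D1 is the Week 37 value in 56%.
- Gap uniform over 0 to 7 days: 95% and 98%.

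**Exposure.** Two full 168-day Parts with 28 days between them give total duration 168+28+168 = 364 days. Percentage of intended dose (SAP 5.6.2) is then (50×336)/(50×364) = 92.3% for a patient who missed nothing.

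**The case against.** The best defence is that long gaps should be rare and little depends on them. The protocol gives 28 days as an outer limit, labels Part 2 C1D1 as Week 25, and lets Part 2 drug be dispensed on the day of Part 1 C7D1 (Table 2, footnote 19). With gaps of a week or less the effect nearly vanishes. Post-Part 1 PRO summaries are descriptive. Worst-value safety summaries use all on-treatment values, and safety listings show both planned and derived visits. All of this stands and limits the size of the point.

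It can also be said that time since randomisation is a legitimate scale, on which Day 240 is nearer Week 37 than Day 268. That is fair as a choice of scale. But SAP 4.2.4 says the windows are there to assign actual visits to protocol-specified visits, and the tables label the slots C2D1, C3D1 and C4D1. On that purpose the rule fails.

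On exposure, SAP 5.6.1 also defines an actual duration net of interruptions, and relative dose intensity uses it. The SAP does not say whether a between-Part gap is recorded as an interruption. The point therefore holds for total duration and percentage of intended dose, and 92.3% still falls in the 80-100% category.

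**Conclusion.** The windows contradict the protocol's own allowance and should be corrected. For patients randomised to ABSK021 who complete Part 1, with C7D1 on Day 169 and on-schedule visits, gaps of 15 to 28 days misfile C2D1 and C3D1 and leave C4D1 unused in the four-weekly columns. The threshold is exact under those assumptions; the number of patients affected is unknown.

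A reader might infer more than the documents support:
- *That Part 3 windows fail too.* No single gap of up to 28 days moves a Part 3 visit.
- *That Week 49 data are widely lost.* The loss is confined to patients with a gap of 16 days or more who do not enter Part 3.
- *That efficacy or durability conclusions are at risk.* The Week 25 tests, ORR and DOR do not depend on these Part 2 windows.
- *That long gaps mark unresolved adverse events.* Nothing in the documents shows this.

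**What to change.** In SAP 4.2.4, apply the first-Part-2-dose windows of Tables 4.4 and 4.5 to every patient who enters Part 2, not only those who leave Part 1 early. C2D1, C3D1, C4D1 and C7D1 then fall on Days 29, 57, 85 and 169, inside windows starting at Days 2, 44, 72 and 128, whatever the Part 1 to Part 2 gap. No separate Part 3 anchor is needed: with a 28-day gap before Part 3, C4D1 is Day 253+28 = 281 (limit 295) and C7D1 is Day 337+28 = 365 (limit 380). The change would also agree with Table 4.1, which already counts placebo switchers from the first Part 2 dose.

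Secondarily, in SAP 5.6.1, sum total duration of exposure by Part so that off-drug days between Parts are excluded from it and from the intended cumulative dose.

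The cost is a short SAP amendment and some reprogramming. The windows already exist, no new data are needed, and the primary analysis does not change.

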4.2.5. PK Concentration Values below Quantification Limit (BQL)

The following rules will be applied to impute any BQL data prior to a descriptive summary and individual plots.

- All BQL values will be set to zero. These BQL will be listed as BQL and tabulated the number of BQL.

Statistical Analysis Plan for Protocol ABSK-021-301

- When more than half (>50%) of the values at a single time point are BQL, mean and median values are reported as BQL. Standard deviation and %CV are not reported; maximum and minimum values are reported as observed (including BQL).

4.3. Data Reporting Convention

4.3.1. General Rules

Unless otherwise specified, tables summarizing disposition, demographics and baseline characteristics will also include an overall column for all patients combined.

In general, continuous variables will be summarized by number of patients with available data (n), mean, standard deviation (SD), median, minimum, and maximum values. Categorical variables will be summarized by the number (n) and percentage of patients in each category. For time-to-event variables, the 25th, median, 75th percentile of the time, and the corresponding 95% confidence intervals (CIs) will be estimated based on Kaplan-Meier method.

All collected data and any derived variables will be presented in patient data listings. A note will be added for any imputed data (e.g., imputed AE start date). Listings will be ordered by region, country, site, patient number, treatment group, planned visit, and assessment or event date, if applicable. The treatment group presented in listings will be based on randomized treatment for efficacy data and demographic and baseline data, and actual treatment received for safety and PK data unless otherwise noted.

The format of tables, figures and listings (TFLs) will be specified in the separate file of TFL mockup. Any rounding will be done after all calculations are made. Precision details refer to [Appendix 2](#) of Section 11.2.

All data processing, summarization and analyses will be conducted using the SAS® system (SAS Institute Inc., Cary, NC) Version 9.4 or above.

